3.9.3 Follow-up period

For the subjects who do not consent to the extension study the SFU visit will take place 20 weeks after the last dose of study medication.

Confidential Page 16 of 63 AEs that occur during the follow-up period will be reported separately. In addition AEs that occur in subjects who have entered the extension study will be captured within the extension study.

3.10 Relative day

The relative day will be included in different listings and will be calculated as follows:

- If the start (stop) date occurred on or after the first dose, but prior to the double-blind drug stop date, relative day is calculated as start (stop) date minus first dose date + 1
- If the start (stop) date occurred after the last dose of double-blind drug, the relative day to the most recent dose is calculated as start (stop) date minus most recent dose date. The relative day in this situation should be preceded by a '+'
- If the start (stop) date occurred before the first dose, the relative day is calculated as start (stop) date minus first dose date. The relative day in this situation should be preceded by a '-'.

For AEs, relative days for start and stop dates will be calculated as the number of days since the first injection of the medication. For non-treatment emergent AEs, relative day of onset will be negative if the event started and stopped before the first dose. Relative day will only be computed for fully completed dates and will be missing for partial dates.

3.11 Changes to protocol-defined analyses

Section 14.6 of the protocol (Handling of dropouts or missing data) describes the sensitivity analysis to be used in this study. More specifically, the protocol describes a sensitivity analysis using multiple imputation as the method for handling missing data and states that the MCMC method will be used for intermittent missing data and that monotone regression will be used for monotone missing data. This SAP has been modified such that the MCMC method will be used for all missing data whether intermittent or monotone.

Section 14.6 of the protocol also notes that the missing data for all continuous efficacy variables that have not been specifically described elsewhere will be imputed using the last observation carried forward (LOCF) approach. This has been updated in this SAP so that these continuous variables will in fact be imputed using the multiple imputation method. However, in the event that multiple imputation is not possible (eg, Due to small group sizes or insufficient missing data) then the LOCF method will be used.

4 STATISTICAL/ANALYTICAL ISSUES

4.1 Adjustments for covariates

The primary efficacy analyses and selected secondary analyses will be adjusted for the following covariates:

- Prior biologic exposure
- Region

4.2 Handling of dropouts or missing data

Based on previous studies of biologics in subjects with moderate to severe chronic plaque psoriasis, it is expected that the number of subjects who discontinue prior to Week 12 will be low. For the small percentage of subjects for whom primary endpoint data are unavailable at Week 12, this lack of data is suggestive of an ineffective study treatment, thereby supporting the imputation of nonresponse. Achieving the clinical response and making it through 12 weeks of study treatment are both critical components of the primary outcome. Therefore, nonresponder imputation (NRI) will be used as the method for handling missing data in the primary analysis. However, to account for other possible mechanisms of missing data other sensitivity analyses will be performed as described in Section 8.1.4.1.

4.2.1 Handling missing data for the primary efficacy variable

For the primary efficacy analysis based on evaluating dose response, missing data will be imputed using NRI. That is, subjects with missing data at Week 12 or who discontinue double blind study treatment prior to Week 12 will be counted as non-responders for the analysis.

In addition, sensitivity analyses will be performed which will assess the impact of different methods of handling missing data. These methods are described in Section 8.1.4.1.

4.2.2 Handling missing data for the secondary analysis of the primary efficacy variable

For the key secondary analysis of the primary efficacy variable based on performing pairwise comparisons of bimekizumab doses versus placebo, missing data will be imputed using NRI as described in Section 4.2.1.

In addition there will be 4 sensitivity analyses to assess the impact of missing data. These are further described in Section 8.1.4.1.

4.2.3 Handling missing data for other efficacy variables

For the dose/exposure response model, missing data will not be imputed. If a subject drops out, this will be used as a covariate in the model. However, the dose/exposure response model is outside of the scope of this SAP and is described in greater detail in a separate data analysis plan (DAP).

Other categorical efficacy variables will be imputed using NRI (ie. Missing data or subjects who prematurely discontinue study treatment prior to Week 12 will be counted as non-responders) or summarized as observed cases. One exception to this rule is the imputation of missing data when summarizing HADS-A and HADS-D scores below 8 (ie. Normal HADS scores). In these summaries, LOCF will be used. That is, the last available HADS-A/HADS-D score while the subject was on study treatment will be carried forward to the missing time points to determine whether or not the subject had normal HADS scores.

Continuous efficacy variables will be imputed using multiple imputation (MI) via the Markov-Chain Monte Carlo (MCMC) method. Summaries based on observed case data will also be prepared.

The MI procedure for continuous efficacy variables (based on MCMC) will be applied as follows using a starting "seed" value of 17402:

Confidential Page 18 of 63

- 1. Create a dataset, one for each treatment group, of subjects with observed values and those needing estimation by multiple imputation. The missing values in each dataset will be filled in using the MCMC method with a total of 100 sets of imputations being performed. Biologic exposure, geographic region and values at baseline and at each post-baseline visit (in chronological order) will be included in the imputation model. If required, in order to facilitate the imputation model, variables can be omitted in the order of biologic exposure and geographical region. Cut-off values will be applied to the imputed data, as appropriate, to ensure that imputed values do not exceed the range of plausible values for the variable being imputed. The resulting datasets for each treatment arm will be combined into one complete dataset based on each of the 100 imputations
- 2. The relevant change from Baseline (or percent change from Baseline) values will then be derived based on the datasets which include observed and imputed values for the variable being considered
- 3. The results from each of the 100 imputed datasets will be combined for the calculation of means and standard errors using Rubin's rules, which account for the uncertainty associated with the imputed values (Rubin, 1987). This will be done using SAS PROC MIANALYZE. For calculation of other descriptive statistics such as the median, min and max, Rubin's rules do not apply. Multiple imputation estimates will be computed by simply averaging the estimates from the m = 1, ..., M independent repetitions of the imputation algorithm:

$$\bar{\theta} = \frac{1}{M} \sum_{m=1}^{M} \hat{\theta}_{m}$$

where $\widehat{\theta}_m$ = estimate of θ from the completed dataset m=1,...,M.

There may be cases where the multiple imputation model fails to converge (eg, sparse subgroups), in such situations the LOCF approach will instead be used to impute the missing data. If LOCF is used instead of multiple imputation for this reason, this will be clearly specified in the corresponding table summary. Should there be no missing data for a study variable then only observed case data will be produced.

Summaries for all variables based on observed case data will also be prepared.

After all enrolled subjects have completed the Week 8 visit, an interim analysis will be performed to analyze the dose-exposure response for PASI, including the PASI90 response, in each dose group to aid in determining the optimal therapeutic dose(s) for subsequent studies. The purpose of performing this analysis at this time is so as to be able to develop a dose-response model in advance of the Week 12 database lock. The final model will include all data up to and including Week 12 and the model will be revised/updated accordingly (if required). The details of this model are outside of the scope of this SAP and are described in a separate DAP.

Decisions related to the conduct of the PS0010 study will not be impacted by these analyses as they will be conducted by individuals that are not part of the clinical study team, and they will not be shared with any clinical study team members until after the database lock, at which point the PS0010 study team will be unblinded.

The database lock to support the development of the PS0010 interim CSR will occur before all subjects have completed the PS0010 study. Specifically, subjects who do not enter the extension study (PS0011) will need to complete the SFU Visit, which occurs 20 weeks after the last dose of study treatment. The Week 12 interim database lock will be performed based on the last subject completing the Week 12 visit. It is anticipated that there will be some subjects still awaiting the SFU at that time. The number of subjects in that position is expected to be low, and the minimal data to be collected from their SFU visits is not considered mandatory to evaluating the key efficacy and safety objectives of the study, therefore it is considered acceptable to proceed with the PS0010 data analysis and interim CSR development in the absence of these data. Once all SFU data have been collected and the full PS0010 study database has been locked, all TLFs will be re-run to include the SFU data that have been added to the database following the Week 12 interim database lick. A final CSR will subsequently be prepared based on this final set of TLFs. Other than the additional data from the pending SFU visits, it is expected that this final CSR will

13 June 2017 PS0010

include biomarker and flow cytometry data summaries that will not be available in the interim CSR. In addition, an independent Data Monitoring Committee (DMC) will periodically review and monitor the safety data from this study and advise UCB.

Details will be provided in the DMC Charter and further details related to this DMC will be outlined in a separate analysis plan.

4.4 Multicenter studies

Not applicable.

4.5 Multiple comparisons/multiplicity

In order to control for the study-wise Type I error rate, the secondary analysis of pairwise comparisons of bimekizumab will be formally evaluated for statistical significance only if the primary efficacy analysis is statistically significant at the 5% 2-sided level. In addition, the pairwise comparisons will follow a sequential testing sequence and the formal evaluation of statistical significance of each comparison is dependent upon the previous comparison achieving statistical significance at the 5% 2-sided level. More details can be found in Section 8.1.3.

4.6 Use of an efficacy subset of subjects

The primary dose response analysis and pairwise comparisons will be repeated using the PPS as a supportive analysis.

4.7 Active-control studies intended to show equivalence

Not applicable.

4.8 Examination of subgroups

Subgroup analyses will be performed on the primary and secondary efficacy variables.

The following variables for subgroup analyses will be used:

- Age (<65 years, ≥65 years)
- Gender (male, female)
- Disease duration (<median, ≥median)
- Region (North America [Canada, USA], Europe & Asia [Czech Republic, Hungary, Poland, Japan]
- Body weight ($<100 \text{ kg}, \ge 100 \text{ kg}$)
- BMI ($<25 \text{ kg/m}^2$, 25 to $<30 \text{ kg/m}^2$, $\ge 30 \text{ kg/m}^2$)
- Prior systemic phototherapy or chemophototherapy (yes, no)

Prior nonbiologic systemic therapy (yes, no)

- Prior biologic therapy (yes, no)
- Prior anti-TNF therapy (yes,no)
- Any prior systemic therapy (yes, no)
- IGA score at baseline (3 vs 4)

- PASI score at baseline ($<20, \ge 20$)
- Psoriasis BSA at baseline (<20%, $\ge 20\%$)

These summaries will be based on imputed data (NRI) and will include descriptive statistics only.

5 STUDY POPULATION CHARACTERISTICS

5.1 **Subject disposition**

itations thereof. Summaries of reasons for screen failures (for all subjects screened), disposition of subjects (for all subjects screened) as well as the subjects who discontinued due to AEs (for the RS) will be produced. The disposition of subjects for all subjects screened will include the number of subjects included in each analysis set (ES, RS, FAS, PPS, SS, PK-PPS, and PD-PPS) overall and by site.

In addition, the number and percentage of subjects who discontinued treatment and who discontinued the study, including a breakdown of the main reason for discontinuation will be presented for subjects in the RS.

5.2 **Protocol deviations**

A summary, using the RS, of the number and percentage of subjects with an important protocol deviation (including a summary of subjects excluded from the PPS due to important protocol deviations) by treatment group and overall and by type of deviation will be provided.

A by-subject listing of important protocol deviations will be provided.

DEMOGRAPHICS AND OTHER BASELINE 6 **CHARACTERISTICS**

Unless specified otherwise all summaries detailed in this section will be performed on the SS and repeated using the FAS. If the SS and FAS analysis sets are identical the summaries will not be repeated.

6.1 Demographics

Demographic variables will be summarized by treatment group and overall.

The following continuous variables will be summarized using descriptive statistics (number of subjects, mean, SD, minimum, median and maximum).

Age at the time of study entry (years)

The following categorical variables will be summarized using frequency counts and percentages.

- Age group (\le 18, 19-<65, \ge 65 years)
- Age group (18 45, 65 45, 285 years)
- Age group ($<40, 40-<65, \ge 65 \text{ years}$)
- Gender
- Race

- Ethnicity
- Height (cm)
- Weight (kg)
- BMI (kg/m^2)

By-subject listings of demographics will be provided.

6.2 Other Baseline characteristics

Baseline characteristics (including Baseline clinical measures) will be summarized by treatment group and overall.

- The following continuous variables will be summarized using descriptive statistics (number of subjects, mean, SD, minimum, median and maximum). Psoriasis BSA (%)
- Duration of disease (in years)
- PASI score
- mNAPSI total score
- PGADA VAS score
- PSSI score
- DLQI total score
- HADS-A score
- HADS-D score

BMI (kg/m²) will be calculated as:

 $BMI = \frac{\text{Weight (kg)}}{(\text{Height (m)})^2}$ (1)

Duration of disease (years) will be calculated as:

$$Disease \ Duration = \frac{\text{(Date of randomization} - Date of onset of Plaque Psoriasis}^1\text{)}}{365.25}$$
 (2)

¹ If the date of onset of plaque psoriasis is partial, it should be imputed to the most recent feasible date (ie, last day of the month if only day is missing, or the last day of the year if day and month are missing).

Should the date of randomization be missing then the duration of disease will be derived using the date of screening.

The following categorical variables will be summarized using frequency counts and percentages.

- Age (<40 years, 40 to <65 years, ≥65 years)
- Region (North America [Canada, USA], Europe & Asia [Czech Republic, Hungary, Poland, Japan]

- Country
- BMI ($<25 \text{ kg/m}^2$, 25 to $<30 \text{ kg/m}^2$, $\ge 30 \text{ kg/m}^2$)
- Duration of disease (<median, ≥median)
- IGA score
- Body weight ($<100 \text{ kg}, \ge 100 \text{ kg}$)
- Prior biologic therapy (yes, no)
- Prior anti-TNF therapy (yes, no)
- Prior phototherapy or chemophototherapy (yes, no)
- Prior nonbiologic systemic therapy (yes, no)
- Any prior systemic therapy (yes, no)
- HADS-A score (<8, 8 to 10, 11 to 14, >14)
- HADS-D score (<8, 8 to 10, 11 to 14, >14)
- Tobacco use (never, current, former)

Aication and any extensions of variations thereof. By-subject listings of Baseline characteristics will be provided

Medical history and concomitant diseases 6.3

All medical history will be listed and the number and percentage of subjects with any medical history will be summarized by treatment group, system organ class (SOC) and preferred term (PT).

Prior and concomitant medications 6.4

Medication start and stop dates will be compared to the date of first dose of treatment to allow medications to be classified as either Prior or Concomitant.

Prior medications include any medications that started prior to the start date of study medication. Past medications are a subset of prior medications, and include prior medications with a stop date before the date of first study medication administration. Concomitant medications are medications taken at least one day in common with the study medication dosing period.

Details of imputation methods for missing or partial dates are described in Section 4.2.4.

The number and percentage of subjects taking Prior medications (excluding past psoriasis medications) will be summarized by treatment group, overall and by ATC class, presenting Anatomical Main Group (ATC Level 1), Pharmacological Subgroup (ATC level 3), and preferred term.

The number and percentage of subjects taking Concomitant medications will be summarized similarly.

Past psoriasis treatment will be captured separately and will also be summarized by treatment group.

13 June 2017 PS0010

A by-subject listing of all Prior and Concomitant medications and of past psoriasis treatment will be provided.

7 MEASUREMENTS OF TREATMENT COMPLICANCE

Due to the method of administration of the treatments, compliance will be examined in terms of completed doses, where one dose will be considered as one complete treatment administration (ie, three injections).

Treatment compliance will be calculated as:

total number of completed doses
$$total number of expected doses$$
 $total number of expected doses$ $total number of expected doses$

where the total number of expected doses is derived relative to when the subject finishes treatment. If a subject completes treatment nine doses are expected (three each at Baseline, Week 4 and Week 8). If a subject discontinues early, then the number of expected injections is based on the time of early discontinuation relative to the dosing visits.

A summary of percent treatment compliance categorized as ≤75% and >75% will be provided by treatment group.

A by-subject listing of treatment compliance will be provided.

EFFICACY ANALYSES 8

Statistical analysis of the primary efficacy variable 8.1

Derivations of PASI score and response 8.1.1

PASI scoring of psoriatic plaques is based on three criteria: redness (R), thickness (T), and scaliness (S). Severity is rated for each index (R, S, T) on a 0-4 scale (0 for no involvement up to 4 for very marked involvement). The body is divided into four areas comprising the head (h), upper extremities (u), trunk (t), and lower extremities (l). In each of these areas, the fraction of total surface area affected is graded on a 0-6 scale (0 for no involvement; up to 6 for 90% - 100% involvement).

The various body regions are weighted to reflect their respective proportion of BSA. The composite PASI score is then calculated by multiplying the sum of the individual-severity scores for each area by the weighted area-of-involvement score for that respective area, and then summing the four resulting quantities as follows (note for R, T, and S scores are as follows: 0 = none, 1 = slight, 2 = moderate, 3 = marked, and 4 = very marked):

$$PASI = (0.1 \times (R_h + T_h + S_h) \times A_h) + (0.2 \times (R_u + T_u + S_u) \times A_u) + (0.3 \times (R_t + T_t + S_t) \times A_t) + (0.4 \times (R_l + T_l + S_l) \times A_l)$$
(4)

where

 R_h , R_u , R_t , R_l = redness score of plagues on the head, upper extremities, trunk, and lower extremities, scored 0-4 respectively;

Confidential Page 25 of 63 T_h , T_u , T_t , T_l = thickness score of plaques on the head, upper extremities, trunk, and lower extremities, scored 0-4 respectively;

 S_h , S_u , S_t , S_l = scaliness score of plaques on the head, upper extremities, trunk, and lower extremities, scored 0-4 respectively;

 A_h , A_u , A_t , A_l = numerical value translation of % area of psoriatic involvement score for the head, upper extremities, trunk, and lower extremities, respectively (where 0 = 0% [clear], 1 = >0% to <10%, 2 = 10% to <30%, 3 = 30% to <50%, 4 = 50% to <70%, 5 = 70% to <90%, and 6 = 90% to 100%).

The highest potential PASI score is 72 for severe disease; the lowest is 0 for no psoriasis lesion. PASI scores are treated as a continuous score, with 0.1 increments within these values. The percent improvement in PASI scores from Baseline will be computed as:

Percent improvement from Baseline =
$$100 \times \frac{Baseline PASI - Post Baseline PASI}{Baseline PASI}$$
 (5)

If a subject has experienced an improvement, this measure will be positive. If a subject has experienced a worsening in their condition, this measure will be negative.

If a subject is missing 1 or 2 severity measurements for a certain region, the average of the remaining severity measurement(s) within that region will be utilized to substitute for the missing severity measurement(s) in that region. If the area of affected skin and/or all severity measurements for up to 2 regions are missing, then the missing (R+T+S) x A for a region will be substituted by the average of the available (R+T+S) x A. Otherwise, the PASI will be set to missing.

A categorical variable, PASI90, is defined to be equal to 1 if the percentage improvement from Baseline in the PASI scores is 90% or greater and 0 if the percentage improvement from baseline is less than 90%. This definition is introduced for the purpose of identifying subjects who respond to the treatment (1 = responder, 0 = non-responder). Similarly, the categorical secondary efficacy variables PASI50, PASI75, and PASI100 response are equal to 1 for subjects with improvements of 50% or greater, 75% or greater and 100% from Baseline in PASI score, respectively (and equal to 0 otherwise),

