### **7.2 Treatments to be administered**

The study medication is to be administered in the clinic by study site staff as 3 sc injections. Suitable areas for sc injections are the lateral abdominal wall and upper outer thigh. During each dosing visit, each of the 3 injections should be administered at a separate injection site. Injection sites should be rotated and injections should not be given into areas where the skin is tender, bruised, red or hard. The injection should last approximately 20 seconds.

Study medication will be administered at Baseline, Week 4, and Week 8. Study medication will also be administered at Week 12 for all subjects entering the extension study. The minimum of time between doses should be no less than 24 days and no more than 32 days.

An IMP Handling Manual will be provided to each site containing instructions regarding drug preparation and dosing.

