10.1.2 Number of doses received

The number of injections received will be summarized by treatment group over the 12 week administration period. There is anticipated to be 3 injections per dosing visit.

Exposure days at risk 10.1.3

For subjects who complete the Week 12 Visit and continue to the extension study, exposure days at risk will be calculated as:

Date of Week 12 Visit 1 Date of first administration of study medication+1 (13) ¹ and the extension study administration of study medication.

For subjects who discontinue on or prior to the Week 12 Visit for reasons other than death, exposure days at risk will be fixed as 84 days (which is equivalent to the intended 12-week initial period). This method is used to provide balance for the comparison of the exposure denominator for the initial period.

For subjects who die prior to the Week 12 Visit, exposure days at risk will be calculated as:

Date of death
$$-$$
 Date of first administration of study medication+1 (14)

Adverse events

Treatment-emergent adverse events

nis docum A-An AE is any untoward medical occurrence in a subject or clinical investigation subject administered a pharmaceutical product that does not necessarily have a causal relationship with this treatment. An AE can therefore be any unfavorable and unintended sign (including an abnormal laboratory finding), symptom, or disease temporally associated with the use of a

> Confidential Page 40 of 63

medicinal (investigational) product, whether or not related to the medicinal (investigational) product.

Treatment-emergent AEs (TEAEs) are defined as those AEs that have a start date on or following the first administration of study treatment through the final administration of study treatment + 140 days (covering the 20-week SFU period). If it is not possible (due to partial dates) to determine whether or not an AE is treatment-emergent then it will be assumed to be a TEAE.

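### SAP 7 mixes doses and injections in treatment compliance; read literally, no subject exceeds 33.3% and the >75% class is empty

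*SAP*

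**What the plan says.** SAP 7 examines compliance by completed doses, "where one dose will be considered as one complete treatment administration (ie, three injections"). The formula divides completed doses by expected doses. For a subject who finishes treatment the same section states: "If a subject completes treatment nine doses are expected (three each at Baseline, Week 4 and Week 8"). For a subject who stops early it changes the unit in the denominator: "then the number of expected injections is based on the time of early discontinuation relative to the dosing visits".

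The result is reported against a single cut: "A summary of percent treatment compliance categorized as ≤75% and >75% will be provided by treatment group". A by-subject listing is also planned.

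Protocol 7.2 specifies three subcutaneous injections at each dosing visit and three dosing visits: "Study medication will be administered at Baseline, Week 4, and Week 8". SAP 10.1.2 is headed as a count of doses, but its text counts injections: "The number of injections received will be summarized by treatment group", and "There is anticipated to be 3 injections per dosing visit".

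Neither SAP 3.11 (changes to protocol-defined analyses) nor the SAP amendment log addresses the compliance rule.

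**The concern.** The numerator is defined in complete administrations, while the expected count of nine only makes sense in injections. Under the SAP's own definition a completer is due three doses. A program written to the text would understate compliance for everyone with at least one completed dose, and would place every subject whose true compliance exceeds 75% in the ≤75% class.

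If the programmer departs from the text and picks a unit, the class of some partly dosed subjects depends on that unrecorded choice. What is at stake is a pre-specified exposure table that would be either meaningless or dependent on an undocumented programming decision.

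**Working it through.** **Inputs**

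- Injections per dose: 3 (SAP 7).
- Dosing visits: 3, at Baseline, Week 4 and Week 8 (Protocol 7.2).
- Injections per dosing visit: 3 (Protocol 7.2; SAP 10.1.2).
- Expected count for a completer: 9, labelled doses (SAP 7).
- Expected count for an early discontinuer: labelled injections, according to the dosing visits due by then (SAP 7).
- Reporting cut: ≤75% versus >75% (SAP 7).

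**Step 1: reproduce the plan's nine.** In injections, 3 visits × 3 injections = 9, which matches. In doses as SAP 7 defines them, 3 visits × 1 dose = 3, which does not. The figure is correct only in injections.

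**Step 2: apply the rule literally.** Compliance = 100 × completed doses / expected count.

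- Completer with 0, 1, 2 or 3 completed doses: 0/9, 1/9, 2/9, 3/9 = 0, 11.1, 22.2, 33.3%.
- Early discontinuer given every due dose, denominator in injections: 1/3 = 33.3% after one visit, 2/6 = 33.3% after two.

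The ceiling is 33.3% and nobody passes 75%. If the discontinuer's denominator were counted in true doses instead, the scores would be 1/1 or 2/2 = 100%, while a fully dosed completer stayed at 33.3%. That is inconsistent in another way.

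**Step 3: compare the two consistent units.**

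| Pattern | Complete doses | Injections | Same class? |
|---|---|---|---|
| Completer, nothing missed | 3/3 = 100% | 9/9 = 100% | yes |
| Completer, one injection missed | 2/3 = 66.7% | 8/9 = 88.9% | no |
| Completer, two missed at one visit | 2/3 = 66.7% | 7/9 = 77.8% | no |
| Completer, two missed at different visits | 1/3 = 33.3% | 7/9 = 77.8% | no |
| Completer, one whole visit missed | 2/3 = 66.7% | 6/9 = 66.7% | yes |
| Two visits due, one injection missed | 1/2 = 50.0% | 5/6 = 83.3% | no |

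For a completer, exceeding 75% takes all three complete doses in one unit and at least 7 of 9 injections in the other.

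**Step 4: count the patterns.** With 0 to 3 injections at each of three visits there are 4 × 4 × 4 = 64 patterns. The class differs in 9: three with one injection missed and six with two missed (three at the same visit, three at different visits). It is the same in the other 55. With two visits due, 2 of 4 × 4 = 16 patterns differ. With one visit due, none do. These are counts of patterns, not weighted by how often they occur, so they do not estimate how many subjects are affected.

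**The case against.** The strongest reply is that the intent is clear. The parenthesis spreading nine as three per visit, the word injections in the next sentence, and the text of SAP 10.1.2 all point to nine injections. A first run showing every fully dosed subject at 33.3% would be noticed at once. Injections are given in the clinic by site staff, so partial administrations may be rare, and without them the two consistent units always agree. No test, error rate or power depends on the table.

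Much of this stands. Nine very probably means injections, the literal table would probably be caught, and the number of subjects affected by the choice of unit may be small. The 33.3% ceiling for early discontinuers also rests on taking the SAP's word injections at face value. The mismatch in SAP 10.1.2 is only a heading; no calculation there is wrong.

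The reply does not settle the rule, however. The numerator is explicitly defined in complete administrations: "where one dose will be considered as one complete treatment administration". Reading nine as injections overrides that definition; reading everything in doses overrides the nine. Either repair discards stated text, and the two repairs can disagree at the only cut the SAP reports.

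**Conclusion.** The concern holds. As written, the compliance rule gives a wrong result: a fully dosed subject scores 33.3% and the >75% class is empty in every arm. This assumes that the discontinuer denominator is in injections, as the SAP words it, and that nobody receives more than the three planned administrations. Subjects truly at or below 75% keep their class, but those with any completed dose get a wrong percentage.

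If a unit is inferred instead, completers who miss one or two of nine injections change class with the choice, as do subjects with two visits due who miss one injection. The documents give no rate of partial administration, so their number is unknown.

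The damage is limited to the descriptive table and the listing. Compliance does not enter the primary logistic model, non-responder imputation, the subgroups or the per-protocol definition as stated. The detailed criteria for important protocol deviations sit in a separate document and could not be checked. The rule should be corrected, but no inference in the trial depends on it.

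**What to change.** State one unit in SAP 7 and use it in both numerator and denominator. Either option works:

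- **Doses:** completed doses over three expected for a completer, or over the number of dosing visits due by discontinuation for an early discontinuer. A visit with only one or two injections then counts as no completed dose.
- **Injections:** completed injections over nine expected for a completer, or over three per dosing visit due for an early discontinuer. Each injection of an incomplete visit then counts.

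The sponsor should choose before unblinding and say explicitly how an incomplete visit is counted, since that is where the options part. As an editorial matter, the heading of SAP 10.1.2 should name the unit its text uses.

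The cost is one sentence in SAP 7 and one heading. No data collection changes.
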